5.11. Procedures for Monitoring Patient Compliance

The investigator will be responsible for monitoring patient compliance with this protocol from the start of the screening period through the EOS visit.

If the investigator or the sponsor determines that the patient is not in compliance with the study protocol, the investigator and the sponsor should determine whether the patient should be withdrawn from the study (Section 4.4). The IEC/IRB/competent authorities should be notified if required by local regulation.

5.12. Randomization and Blinding

This is a randomized, double-blind study. Patients who meet all inclusion criteria, none of the exclusion criteria, and all of the randomization criteria will be randomly assigned to receive TEV-48574 or placebo to match TEV-48574 in a 1:1 ratio.

Patients will be randomly assigned to treatment groups by means of a computer-generated randomization list. The specifications for randomization will be under the responsibility and oversight of Teva Global Statistics.

The study patients and the clinical team at the site will be blinded to treatment assignment until the database is locked for analysis. Individuals who may not be blinded include (but are not limited to) the bioanalytical scientists, pharmacokineticists, and biostatisticians who are not directly involved in study conduct.

The randomization list will be assigned to the relevant treatment groups through a qualified service provider, eg, via the Randomization and Trial Supply Management (RTSM) system. The generation of the randomization list and management of the RTSM system will be done by a qualified service provider under the oversight of the responsible function at Teva.

5.13. Maintenance of Randomization and Blinding

5.13.1. Maintenance of Randomization

Patient randomization codes will be maintained in a secure location at the service provider contracted to generate the codes. At the time of analysis (after the end of study), after receiving unblinding request from Teva statistician, the service provider will provide the unblinded IMP assignment according to the processes defined in the relevant Standard Operating Procedure (SOP).

5.13.2. Blinding and Unblinding

Blinded pharmacokinetic and immunogenicity data may be assessed during the study. For patients who have pharmacokinetic or immunogenicity sample bioanalysis or data analysis conducted, the individuals responsible for sample bioanalysis and other responsible personnel will know who received test IMP and who received placebo IMP during the study (of those patients only). Personnel responsible for bioanalysis will be provided with the randomization code to facilitate the analysis. However, the personnel responsible for bioanalysis and pharmacokinetic data analysis will not have access to clinical safety and efficacy data, and will provide concentration data to other personnel in a manner that will not identify individual patients (ie, a dummy patient identifier will be linked to the concentration data of an individual patient).

Pharmacokinetic sample analysis by the bioanalytical laboratory and pharmacokinetic parameter calculations by pharmacokineticists will be performed during the course of the study. The population pharmacokinetic model for TEV-48574 may be updated with new pharmacokinetic data emerging from the ongoing study. The process to ensure study integrity, maintenance of the double blind, and the responsibilities of the relevant study personnel will be described in a pharmacokinetic analysis plan that will be approved prior to any data transfer, per the sponsor's relevant SOP(s) (eg, GBP-RD-502 [Performing Pharmacokinetic Analyses While Maintaining

the Blind]). A similar process could be implemented for the pharmacokinetic/pharmacodynamic model with updated pharmacokinetic and pharmacodynamic data, based on availability of the appropriate SOP.

In case of a serious adverse event, pregnancy, or in cases when knowledge of the IMP assignment is needed to make treatment decisions, the investigator may unblind the patient's IMP assignment as deemed necessary, mainly in emergency situations. Individual randomization codes, indicating the IMP assignment for each randomized patient, will be available to the investigator(s) or pharmacist(s) at the investigational center via the RTSM, both via telephone and internet. Breaking of the treatment code can always be performed by the investigator without prior approval by the sponsor; however, the sponsor should be notified following the breaking of the treatment code. The patient's IMP assignment should not be revealed to the sponsor.

When a blind is broken, the patient will be withdrawn from the study and the event will be recorded on the CRF. The circumstances leading to the breaking of the code should be fully documented in the investigator's study files and in the patient's source documentation. Assignment of IMP should not be recorded in any study documents or source document.

For an adverse event defined as a suspected unexpected serious adverse reaction (SUSAR) (ie, reasonable possibility; see Section 7.1.4), Global Patient Safety and Pharmacovigilance (GPSP) may independently request that the blind code be broken (on a case-by-case basis) to comply with regulatory requirements. The report will be provided in an unblinded manner for regulatory submission. If this occurs, blinding will be maintained for the investigator and for other personnel involved in the conduct of the study, and analysis and reporting of the data.

The JDMC will review data in a blinded fashion, as outlined in [Appendix B](#).

An interim analysis (Section 9.12) will be conducted by an independent, unblinded statistician who is not a part of the study team. A group of the sponsor's management team who are not a part of the study team may have access to the unblinded interim analysis results. A communication plan to ensure the maintenance of the study blind among the blinded personnel involved in the conduct of the study will be put in place prior to the interim analysis.

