3.6.1.2.9. Early Termination (ET) Visit

Patients who discontinue treatment with IMP for reasons other than the occurrence of LoAC/CAE in the study are encouraged to complete early termination (ET visit) procedures as soon as possible after receiving their last dose of IMP and to complete the remaining study visits and assessments (with the exception of administration of IMP) including EOT and EOS within the original time frames based on day of randomization (DoR). These patients are not considered to have withdrawn from the study.

Patients who decide to withdraw completely from the study are encouraged to complete early termination (ET visit) procedures as soon as possible after receiving their last dose of IMP.

At the ET visit the following procedures/assessments will be performed:

- Perform concomitant medication inquiry.
- Perform adverse event inquiry.
- Perform COVID-19 symptoms inquiry.
- Review daily e-diary for SABA/quick-relief medication usage and nighttime awakenings, including for adherence.

- Review daily hand-held spirometry, including for adherence.
- Perform LoAC and CAE inquiry.
- Complete the ACQ-6.
- Check supply and, if required, dispense study-provided controller therapies (for patients who remaining in the study). Collect returned inhalers.
- Check supply of study-provided SABA (for patients who are remaining in the study). Collect returned inhalers.
- Perform ECG.
- Perform vital signs measurements (includes systolic and diastolic blood pressure, pulse, body temperature, and respiratory rate).
- Perform full physical examination.
- Measure FeNO.
- Perform in-office spirometry (full flow-volume loop).
- Perform urine pregnancy testing (women of childbearing potential).
- Collect samples for clinical laboratory tests (serum chemistry, CBC with differential count, peripheral eosinophil count, urinalysis).
- Collect blood for serum TEV-48574 concentration determination (PK assessment) from all patients.
- Collect blood sample for immunogenicity (ADA) assessment.
- Collect blood sample for ██████████ assessment.

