3.6.1.3. Assessments and Procedures During Follow-up

3.6.1.3.1. Assessments and Procedures at the End of Study Visit

At 24 weeks after randomization (± 7 days), patients will return to the study center for the EOS visit.

All patients, including those who discontinued treatment whether for protocol-defined LoAC or other reasons, should complete the End of Study (EOS) visit. Patients who complete the EOS visit are considered to have completed the study.

The monitoring of patients with ongoing adverse events or clinically significant abnormal laboratory test results (as interpreted by the investigator) at the EOS is described in Section 7.1.2.

Efforts should be made to perform the following assessments and procedures in the order listed at the EOS visit (week 24):

- Perform concomitant medication inquiry.
- Perform adverse event inquiry.
- Perform COVID-19 symptoms inquiry.
- Review daily e-diary for SABA/quick-relief medication usage and nighttime awakenings, including for adherence.
- Review daily hand-held spirometry, including for adherence.

Clinical Study Protocol with Amendment 02

- Collect e-diary and hand-held spirometer
- Perform LoAC and CAE inquiry.
- Complete the ACQ-6.
- Collect any study-provided inhalers.
- Perform ECG.
- Perform vital signs measurements (includes systolic and diastolic blood pressure, pulse, body temperature, and respiratory rate).
- Perform full physical examination and document body weight.
- Measure FeNO.
- Perform urine pregnancy testing (women of childbearing potential).
- Collect samples for clinical laboratory tests (serum chemistry, CBC with differential count, peripheral eosinophil count, urinalysis).
- Collect blood for serum TEV-48574 concentration determination (PK assessment) from all patients.
- Collect blood sample for immunogenicity (ADA) assessment.
- Collect blood sample for ██████████ assessment.

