4.4. Withdrawal Criteria and Procedures for the Patient

4.4.1. Withdrawal Criteria

In accordance with the Declaration of Helsinki (in accordance with the applicable country's acceptance) patients may completely withdraw from the study (ie, with no further study participation or contact) at any time for any reason. Patients may also voluntarily discontinue IMP and remain in the study for assessments. The investigator and/or sponsor may also discontinue a patient from IMP and/or withdraw a patient from the study, eg,

- in the event of intercurrent illness, adverse events, pregnancy, or any other reason concerning the health or well-being of the patient that indicates to the investigator that continued participation is not in the best interest of the patient, or

- if the patient is noncompliant with the study procedures and assessments or protocol-defined study restrictions or prohibited concomitant medication

Investigators are to discuss patients who may be considering discontinuing IMP or withdrawing completely from the study with the sponsor as soon as the site becomes aware of the situation.

Investigators should attempt to obtain information on patients in the case of withdrawal from the study or discontinuation from IMP. Results of any evaluations and observations, together with a narrative describing the reason(s) for withdrawal from the study or discontinuation from IMP, should be recorded in the source documents. The case report form (CRF) should document the primary reason for withdrawal from the study or discontinuation from IMP.

Discontinuation of IMP as described above and below does not include patients who discontinue IMP due to a LoAC event, as LoAC events are part of the planned conduct of the study.

If an adverse event is the primary reason for discontinuation of IMP or withdrawal from the study, this should be documented in the source and in the CRF including test results if applicable. Under these circumstances, monitoring should be continued until the event has resolved or stabilized, or until the patient is referred to the care of a health care professional, or until a determination of a cause unrelated to the study drug or study procedure is made.

The investigator should inform the sponsor as soon as possible of each patient who is being considered for withdrawal due to adverse events. Additional reports should be provided when requested.

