4.4.2. Discontinuation of IMP

Patients who discontinue treatment with IMP while remaining in the study are encouraged to complete early termination (ET visit) procedures as soon as possible after receiving their last dose of IMP and to complete the remaining study visits and assessments (with the exception of administration of IMP) including EOT and EOS within the original time frames based on date of randomization (DoR). The investigator should determine the reason for and the date of discontinuation of study treatment and record this information in both the source documentation and the CRF. The patient should not be considered withdrawn from the study due to interruption or discontinuation of IMP.

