### **8.3. Adverse Events**

Adverse events will be recorded from time informed consent is obtained through the end of study participation.

All adverse events will be coded using MedDRA. Each patient will be counted only once in each preferred term or SOC category for the analyses of safety. Summaries will include treatment-emergent adverse events which are defined as adverse events occurring at or after the first dose of the IMP through the end of the follow-up visit. Listings will include all adverse events recorded.

Summaries will be presented for all adverse events (overall and by severity), adverse events determined by the investigator to be related to test IMP (defined as related or with missing relationship) (overall and by severity), adverse events determined by the investigator to be related to the medical device, or the study inhaler (defined as related or with missing relationship), serious adverse events, and adverse events causing drug withdrawal or discontinuation from the study. Adverse events with the missing flag indicating serious will be excluded from the summary of serious adverse events but included in the summary of non-serious adverse events.

Summaries for clinical asthma exacerbation related adverse events, loss of asthma control related adverse events, injection site reaction adverse events, protocol-defined adverse events of special interest (PDAESI), PDAESI require completion of suspected anaphylaxis will also be presented.

Listings for deaths, serious adverse events, adverse events leading to drug withdrawn or the study discontinuation, clinical asthma exacerbation related adverse events, loss of asthma control

related adverse events, injection site reaction adverse events, PDAESI, and PDAESI require completion of suspected anaphylaxis, adverse event required concomitant or additional treatment will be presented. In addition, listings for MedDRA dictionary terms for adverse event descriptions and adverse event preferred terms by patient number and treatment group will be presented.

Adverse events for patients who did not meet screening criteria will be listed.

In additional, adverse events and serious adverse events occurred during the 10 weeks period after the last dose of IMP will be summarized using descriptive statistics. These adverse events will be presented in a patient listing as well. Injection Site Assessments

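### An investigator code break takes the patient out of the study, so the remaining scheduled visits and EOS are no longer planned, unlike for a patient who only stops IMP

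*Protocol*

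**What the plan says.** Protocol 5.13.2 names three triggers (a serious adverse event, a pregnancy, or a treatment decision that needs the assignment) and allows the investigator to unblind the patient's "IMP assignment as deemed necessary, mainly in emergency situations". The consequence follows: "When a blind is broken, the patient will be withdrawn from the study and the event will be recorded on the CRF". A sponsor code break for a SUSAR is handled separately there and leaves the investigator blinded, so this point concerns investigator code breaks only.

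For a patient who stops IMP but stays in, 4.4.2 encourages an ET visit and encourages the patient "to complete the remaining study visits and assessments (with the exception of administration of IMP) including EOT and EOS". Section 3.6.1.3.1 adds: "All patients, including those who discontinued treatment whether for protocol-defined LoAC or other reasons, should complete the End of Study (EOS) visit".

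For a patient who leaves the study, 3.6.1.2.9 says: "Patients who decide to withdraw completely from the study are encouraged to complete early termination (ET visit) procedures as soon as possible". Section 4.4.3 adds that participation then ceases and later visit data count as missing.

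On the AE recording period, SAP 8.3 says: "Adverse events will be recorded from time informed consent is obtained through the end of study participation". The same section plans a further summary: "adverse events and serious adverse events occurred during the 10 weeks period after the last dose of IMP will be summarized".

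**The concern.** A code break is usually prompted by a safety event. The rule therefore shortens planned follow-up in the patients for whom further safety information is most wanted. Those patients still enter the treatment-emergent AE tables and the 10-week post-dose summary alongside patients who stopped IMP for other reasons. New AEs would be sought less systematically in the first group than in the second.

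The 10-week window is not arbitrary: Protocol 7.3 equates about 10 weeks with five half-lives, so the missing contacts can fall while drug is still present. Protocol 7.1.7 also leaves it to the investigator and sponsor to decide, after an AE or emergency, whether the patient continues in the study. Section 5.13.2 removes that choice once the code is broken.

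**Working it through.** The plan states no figure to reproduce. The check is a reading of the text followed by a count from the visit schedule.

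**1. Does 5.13.2 mean the study, or only IMP?** Section 4.4.1 lists stopping IMP and withdrawing from the study as separate actions, and describes complete withdrawal as the end of participation and contact. Section 4.4.2 says that stopping IMP is not withdrawal. So 5.13.2 cannot be read as loose wording for stopping IMP.

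**2. What follow-up remains after the break?**
- Index AE: 4.4.1 says "Under these circumstances, monitoring should be continued until the event has resolved or stabilized", and 7.1.2 requires AE questioning at every contact, so these follow-up contacts can also pick up new events.
- PK and ADA: extra samples are sought at an SAE or suspected hypersensitivity (Table 3 footnotes, 8.1, 8.2). For anaphylaxis, ADA sampling is sought up to 30 days after onset.
- Pregnancy outcome (7.3), and SAEs that come to the investigator's attention (7.1.5.3.1).
- An encouraged ET visit with AE inquiry, chemistry, CBC, PK and ADA (3.6.1.2.9).

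No section keeps the remaining scheduled visits or EOS for this patient.

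**3. Scheduled items no longer planned.** Inputs are Protocol Tables 3 and 4 and SAP Table 1: V1 day 1, V2 15, V3 29, V4 43, V5 (phone) 50, V6 57, V7 71, V8 85, V9 99, V10 113, V11 (EOS) 169. AE inquiry is at every contact. PK/ADA is at V1, V2, V3, V6, V8, V10 and V11. Chemistry/CBC is at V1, V3, V6, V8, V10 and V11. Doses are given at V1 to V4 and V6 to V9.

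For a break after visit k and before the next visit, contacts lost = 11 − k. PK/ADA and laboratory losses are the scheduled time points after visit k. The window columns count items on or before last dose + 70 days, for a patient dosed on schedule up to the break. The ET visit is left out because it is encouraged on both routes.

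| Break after | Contacts | PK/ADA | Chem/CBC | Last dose + 70 | Contacts in window | PK/ADA in window |
|---|---|---|---|---|---|---|
| V1 | 10 | 6 | 5 | day 71 | 6 | 3 |
| V2 | 9 | 5 | 5 | day 85 | 6 | 3 |
| V3 | 8 | 4 | 4 | day 99 | 6 | 2 |
| V4 | 7 | 4 | 4 | day 113 | 6 | 3 |
| V5 | 6 | 4 | 4 | day 113 | 5 | 3 |
| V6 | 5 | 3 | 3 | day 127 | 4 | 2 |
| V7 | 4 | 3 | 3 | day 141 | 3 | 2 |
| V8 | 3 | 2 | 2 | day 155 | 2 | 1 |
| V9 | 2 | 2 | 2 | day 169 | 2 | 2 |
| V10 | 1 | 1 | 1 | day 169 | 1 | 1 |

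Example, break after V1: last dose is day 1, so the window closes on day 71. V2 to V7 fall inside it, giving 6 contacts, with PK/ADA at V2, V3 and V6.

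The PK/ADA columns matter only on active drug, because placebo samples are not analysed (8.1, 8.2).

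**4. Patients affected.** The unblinding rate is an assumption, 1% to 3%.
- 124 randomized: 0.01 × 124 = 1.2 to 0.03 × 124 = 3.7
- 174 randomized: 0.01 × 174 = 1.7 to 0.03 × 174 = 5.2
- On active drug, if code breaks are balanced: half of 1.2 to 3.7, or 0.6 to 1.9 of 124

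**5. Primary analysis.** SAP 1.7 closes each patient's treatment period 14 days after the last dose. It counts a patient who stops treatment or leaves the study without LoAC, for reasons other than lack of efficacy or an asthma-related AE, as having no LoAC. Both routes give the same result, except for a LoAC that occurs after the break but within those 14 days.

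**The case against.** The strongest case for leaving the rule alone is that it is a deliberate trade-off. LoAC is determined by the investigator (SAP 6.2.1), and AE relatedness is also an investigator judgement. Keeping an unblinded patient in the study admits unblinded assessments, and the ITT set includes data after treatment discontinuation. This stands as a real but small cost. It argues for dating and flagging the data; it does not justify ending scheduled safety visits.

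The loss is also partly an inference. Section 4.4.3 is written for a patient's own decision to leave, no sentence spells out the visit schedule after a code break, and 3.6.1.3.1 opens with all patients. That section, however, goes on to name treatment discontinuers and not withdrawn patients, and no other procedure covers a patient withdrawn by rule. At best the follow-up is unspecified. The comparison route in 4.4.2 is itself only encouraged, so the counts above are upper limits.

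Numbers will be small. The plan already allows 15% dropout (0.15 × 124 = 18.6 patients), Phase 1 reported no SAEs (1.2.2), and usual-course exacerbations are kept out of SAE reporting. All of this limits the size.

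Two stronger readings are tempting and should not be drawn. A reader might infer that safety follow-up stops at the code break; the elements that remain under item 2 of the working show otherwise. A reader might also infer that exclusion criterion k, which removes a pregnant woman from the study, contradicts 7.3, which stops IMP. The two differ, but both can be followed: leaving the study includes stopping IMP, 7.3 itself provides for complications learned of after withdrawal, and the pregnancy is followed either way.

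**Conclusion.** The point holds in a limited form. After an investigator code break the protocol no longer plans the remaining scheduled contacts, EOS, or their AE inquiry and laboratory time points, whereas it asks IMP discontinuers to complete them. The nominal loss is at most 10 contacts and falls to 1 depending on timing; inside the 10-week post-dose window it is at most 6. These figures assume full attendance on the 4.4.2 route and dosing on schedule up to the break. The number of patients, about 1 to 4 of 124 (2 to 5 of 174), rests on the assumed 1% to 3% rate.

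The consequence is less complete safety ascertainment in a few patients selected by a safety event. A reader might infer that the primary comparison is biased; SAP 1.7 does not support that, because the two routes can differ only through a LoAC within 14 days of the last dose. This is an inexpensive improvement worth making, and it does not threaten the trial's main result.

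**What to change.** Reword 5.13.2: when the investigator breaks the code, IMP is discontinued and the patient stays in the study. The patient is asked to attend the ET visit and to continue safety follow-up through EOS by the 4.4.2 route. The CRF entry that 5.13.2 already requires should carry the unblinding date, and data after that date should be flagged. A half-sentence could confirm that the rule applies to investigator code breaks. Section 4.4.1 needs no change.

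The cost is a few sentences and one CRF date field. The downside to state openly is that later AE causality and LoAC judgements for that patient are made by an unblinded site.

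As an optional tidy-up, harmonise exclusion k (4.2 and the synopsis) with 7.3, so that both say IMP is stopped and the patient and pregnancy are followed.
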